#### **9.1.3.1 All Study Subjects**

##### **9.1.3.1.1 Baseline Assessments (Day 1)**

Baseline (Day 1) for this long-term extension study is defined in [Section 9.1.1](#).

Prior to IMP administration, the assessments and procedures listed in [Table 9-1](#) will be performed and include:

- Obtain and document written informed consent.
- Check inclusion and exclusion criteria (see [Section 9.3.1](#) and [Section 9.3.2](#)).

Discontinue IMP for subjects who fail to show clinical response to treatment (as defined in [Section 9.3.1](#) for PsA subjects), in accordance with the IVRS instruction (see [Section 9.3.5](#)).

- Demographics to include body weight and height only. Date of birth, sex, and ethnicity will be obtained from the parent study.
- Record physical examination findings.
- Record medical and medication history (including any AEs or concomitant medications that remain ongoing from the parent study or any relevant observations made at the Baseline visit prior to signing the Informed Consent Form (ICF) for this long-term extension study [including laboratory test results from Week 48 of the parent study] are to be recorded).
- Perform a urine pregnancy test by urine dip stick (at the site using materials supplied by the central laboratory).
- Perform safety assessments including:
  - 12-lead ECG,
  - vital signs,
  - C-SSRS,
  - routine safety laboratory assessments (hematology, chemistry, and urinalysis.). Blood samples are to be collected (pre-dose) after ECG and vital sign measurements,
  - lipids (blood samples are to be collected [pre-dose] after 12 hours fasting and after ECG and vital sign measurements),
  - erythrocyte sedimentation rate (ESR) will be performed at the site using materials supplied by the central laboratory. High sensitivity C-reactive protein (hsCRP) samples will be sent to the central lab and analyzed by central lab.

These hsCRP/ESR measures will be used for determination of potential AEs should they rise unexpectedly.

- Obtain a PK sample for drug concentration.
- Obtain a blood sample for ADA testing.

Following completion of all assessments and providing all study criteria are met, administer the first dose of IMP for the long-term extension study (Baseline, Day 1). Following IMP administration, complete the following assessments:

- AEs,
- Record concomitant medications.

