### **12.3 Description of Statistical Analyses**

All the safety and efficacy data will be summarized descriptively through appropriate data tabulations and descriptive statistics. For continuous variables, unless otherwise stated, the number of available observations (n), mean, standard deviation (SD), median, and range will be provided. For categorical variables, the number and percentage in each category will be displayed.

The last value of a variable taken before the first dose of IMP in parent study will be used as the original Baseline value. The last value before the first dose of IMP in the long-term extension study will be used as the LTE Baseline value. Unless otherwise specified, missing or dropout data will not be imputed for the purpose of data analysis.

A more detailed description of study analyses will be presented in the Statistical Analysis Plan (SAP).

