# Statistical Analysis Plan (SAP)

## 4 STUDY ENDPOINTS

### 4.1 Efficacy endpoint

The efficacy endpoints are:

- The proportion of subjects who achieve ACR20 at measured time points,
- The proportion of subjects who achieve ACR50 at measured time points,
- The proportion of subjects who achieve ACR70 at measured time points,
- Individual components of ACR response at measured time points:
  - tender joint counts (68),
  - swollen joint counts (66),
  - PGA of disease activity (VAS),
  - PtGA of disease activity (VAS),
  - patient's pain assessment (VAS),
  - patient's self-assessed disability (HAQ-DI),
  - acute-phase hsCRP,
  - ESR.
- SF-36 at measured time points.

The ACR20 is defined as at least a 20% improvement from Baseline in both tender joints (68) and swollen joints (66) along with at least a 20% improvements in 3 of 5 other items: 1) the Physician Global Assessment (PGA) of disease activity (as measured using a VAS), 2) the Patient Global Assessment (PtGA) of disease activity (as measured using a VAS), 3) patient pain assessment (as measured using a VAS), 4) patient self-assessed disability (as measured using the HAQ-DI), and 5) acute-phase CRP.

Similarly, ACR50 is defined as at least a 50% improvement from Baseline in both tender joints (68) and swollen joints (66) along with at least a 50% improvements in 3 of 5 other items listed above; ACR70 is defined as at least a 70% improvement from Baseline in both tender joints (68) and swollen joints (66) along with at least a 70% improvements in 3 of 5 other items listed above.

Baseline used to derive ACR is the baseline value for each component from parent study.

If the value in any of the components at a time point is missing, the component variables that are not missing will be used to determine the response status. As a general principle, if there are sufficient

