# Statistical Analysis Plan (SAP)

## 7 STATISTICAL CONSIDERATIONS AND ANALYSIS

### 7.1 Derived variables

Details for deriving efficacy variables are discussed in [Sections 4.1, 4.2](#), and [4.3](#). The below set of variables are the basic demographic variables and some general variables.

Variables	Formula
Age at informed consent (in years)	year of informed consent – year of birth
Body mass index (BMI;kg/m  )	weight (kg)/[height (m)] 
Extension Study day at any visit	(visit date – date of first IMP administration in the extension study) + 1 for visit dates on or after first IMP dosing date in the extension study; (visit date – date of first IMP administration in the extension study) for visit dates before first IMP dosing date in the extension study
Parent Study day at any visit	(visit date – date of first IMP administration in the parent study) +1 for visit dates on or after first IMP dosing date in the parent study; (visit date – date of first IMP administration in the parent study) for visit dates before first IMP dosing date in the parent study
Change from baseline	Post baseline value – Baseline
Percent change from baseline#	[(Post baseline value – Baseline)/Baseline]*100

#: If the baseline value of any component of ACR is equal to 0, the following algorithm will be used in evaluating the percent change from baseline: If change from baseline is also equal to 0, then percent change from baseline is set to be 0%; If change from baseline is > 0, then percent change from baseline is set to be 9999999%. Note: these conventions are only used when deriving ACR20/50/70 and will be described in the ACR listing. Such values will be flagged and explained in the footnote for presentation in the ACR listing.

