# Statistical Analysis Plan (SAP)

## 8 STATISTICAL METHODS

### 8.1 General Statistical Conventions

All statistical procedures will be completed using SAS version 9.4 or higher.

Continuous variables will be summarized using descriptive statistics, including number of subjects (n), mean, median, standard deviation (SD), minimum and maximum. One additional decimal point for mean and median and 2 additional decimal points for SD will be used.

For categorical variables, summaries will include counts of subjects and percentages. Percentages will be rounded to one decimal place.

Two-sided 95% confidence intervals (CI) will be provided when relevant.

For summary purposes, baseline will be defined as the last available value prior to the date of first IMP administration in parent study.

For reporting purpose, summary tables for efficacy variables and safety variables will be displayed by nominal visit as appropriate. Unscheduled assessments will not be included in the summary tables, but will be in data listings.

All subject data, including those derived, will be presented in individual subject data listings. Unless otherwise stated, unscheduled visit results will be included in date/time chronological order, within patient listings only. All listings will be sorted by treatment group, subject number, date/time and visit. The treatment group as well as patient's sex and age will be stated on each listing. Unless otherwise stated, data listings will be based on ASaT population.

The treatment groups will be displayed in the format below in tables:

- 200 mg Tildrakizumab q4wk
- 200 mg Tildrakizumab q12wk
- 100 mg Tildrakizumab q12wk

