### 8.4.2 Baseline characteristics

Tender joint counts, swollen joint counts, PGA of disease activity, PtGA of disease activity, patient's pain assessment, HAQ-DI, hsCRP, ESR, and SF-36 at baseline will be summarized. Note baseline is the Baseline values from parent study.

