## 8.7 Safety analyses

Safety analyses will be conducted on the ASaT population and will be performed for all safety variables specified below.

The subjects will be summarized based on the actual treatment received at the beginning of the extension study.

The safety analyses of changes from baseline to a specific time point in safety variables (e.g., laboratory parameters, vital signs, and ECG) will only include subjects from ASaT who have data available for both the baseline and the time point under consideration unless otherwise specified. Where relevant, temporal relationships to parent study baseline will be described.

No statistical tests will be performed.

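### SAP 8.1 cuts baseline off at the date of first parent-study IMP, while protocol 12.3 cuts it off at the first dose; read literally, the SAP excludes same-day pre-dose values

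*SAP*

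**What the plan says.** SAP 8.1 sets the general convention for summaries: "baseline will be defined as the last available value prior to the date of first IMP administration in parent study". The cut-off is a calendar date.

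Protocol 12.3 gives two definitions, both cut off at the dose. For the parent study: "The last value of a variable taken before the first dose of IMP in parent study will be used as the original Baseline value". For the extension: "The last value before the first dose of IMP in the long-term extension study will be used as the LTE Baseline value". SAP 8.1 has no counterpart to the second.

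Elsewhere the SAP refers to the parent study's own baseline without a date rule. SAP 4.1: "Baseline used to derive ACR is the baseline value for each component from parent study". SAP 8.4.2: "Note baseline is the Baseline values from parent study". SAP 8.8.2 describes baseline ADA samples as taken before dosing, and its Table 2 classifies subjects by pre-treatment samples.

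SAP 8.7 limits change-from-baseline safety analyses: they "will only include subjects from ASaT who have data available for both the baseline and the time point under consideration". SAP section 1 says the SAP supersedes the protocol's statistical considerations and will identify substantial differences. SAP section 10 lists none.

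**The concern.** A value measured on the first dosing day, before the injection, is a baseline value under the protocol and is not one under the SAP wording. Because the SAP says that it takes precedence, a programmer who follows it would code assessment date earlier than dose date.

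If parent Baseline assessments shared the date of the first dose, two things follow. A variable also measured at screening falls back to that older value. A variable measured only on Day 1 has no baseline. SAP 7.2.1 in general does not impute, and SAP 8.7 then removes the subject from the change tables. The tables concerned are those for laboratory tests, vital signs and ECG and the C-SSRS worst-case shift table. Changes in these four are named in the primary safety objectives (protocol 8.1, SAP 2.1), and protocol 9.2 presents comparison with the original parent Baseline as a feature of the design.

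**Working it through.** The documents give no figure to reproduce, so the check sets the wording side by side.

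**1. Study-day scale.** SAP 7.1 computes parent study day as visit date minus first-dose date plus 1 "for visit dates on or after first IMP dosing date in the parent study", and without the plus 1 for earlier dates. Let D be the first-dose date.
- A visit on D: (D − D) + 1 = day 1.
- A visit the day before: (D − 1) − D = day −1.
- There is no day 0, and the formula carries no time of day.

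**2. Apply each rule to a value taken on D before the injection.**

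| Rule | Test | Result |
|---|---|---|
| SAP 8.1 | D < D | false: excluded; fall back to day −1 or earlier, or missing |
| Protocol 12.3 | pre-dose time < dose time | true: this value is baseline |

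The rules therefore differ for every variable assessed pre-dose on parent Day 1, and agree for every variable whose last pre-treatment value fell on an earlier date.

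**3. Does another SAP passage restore same-day values generally?** None does. SAP 4.1 and 8.4.2 point to the parent Baseline values for ACR and for baseline characteristics. SAP 8.8.2 covers ADA. Nothing comparable covers laboratory tests, vital signs, ECG or C-SSRS, so these rest on 8.1 alone.

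**4. Was parent Baseline a dosing visit?** Two pieces of indirect evidence:
- SAP 3.3, describing the two q12wk arms, has the interim 4-weekly placebo injections start at the parent study's Baseline. That reads as an injection visit, although the sentence sits in a description of the extension's dosing.
- In the extension, assessments and first dose share one visit (protocol 9.1.3.1.1): "Following completion of all assessments and providing all study criteria are met, administer the first dose of IMP for the long-term extension study". This shows practice in this study, not in the parent.

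The parent schedule itself is not available. It is also unknown which variables were measured at parent screening, at Baseline, or at both.

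**5. Range of effect.**
- Lower end: nil, if every parent baseline measure was dated before the first dose.
- Upper end: a screening value in place of the Day 1 value, or a missing baseline, for every subject assessed pre-dose on Day 1.

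**The case against.** The strongest reply is that this is loose drafting. SAP section 10 reports no departure from the protocol, SAP 4.1, 8.4.2 and 8.8.2 all fit the protocol's rule, and the author probably meant before the first dose. That may well be so, but it does not remove the problem: the sentence as written gives a different result, and the SAP claims precedence over the protocol.

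The reply also rightly limits the consequences. Several stronger readings are tempting and the documents do not support them:

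- *That ACR20/50/70 responses would change or lose their denominators.* SAP 4.1 is the more specific provision and points to the parent baseline value of each component. What stands is a conflict between 4.1 and 8.1, not a demonstrated change in any response. ACR is also a legacy analysis here, since the amended protocol removed the efficacy objectives.
- *That ADA status is affected.* SAP 8.8.2 and its Table 2 already work from samples taken before dosing.
- *That all 286 subjects are affected.* That number is a ceiling on enrolment, and the share with Day 1 pre-dose values is unknown.
- *That safety results as a whole are undermined.* AE incidence and exposure-adjusted rates do not use this baseline; SAP 8.7.1 defines TEAEs from the date of extension consent. The affected tables are descriptive, with no tests.

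Finally, a variable with every baseline missing would be noticed at programming. A screening value silently replacing a Day 1 value would be much harder to see.

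**Conclusion.** The conflict is real and undeclared. Read literally, SAP 8.1 admits only parent study day −1 or earlier, while protocol 12.3 also admits pre-dose values on the first dosing day.

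For laboratory tests, vital signs, ECG and C-SSRS, the effect lies anywhere between nil and an older or missing baseline for every subject assessed pre-dose on parent Day 1. Any effect above nil assumes that parent Baseline assessments were made on the date of the first dose, which SAP 3.3 suggests but does not prove. For ACR and baseline characteristics, the SAP is inconsistent with itself. ADA needs no change.

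The sentence should be corrected, because it governs tables tied to the primary safety objectives. It does not put any hypothesis test or AE rate at risk.

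**What to change.** Replace the SAP 8.1 sentence with:

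> Baseline is the last non-missing value before the first IMP administration in the parent study, including pre-dose values on the day of first dosing (by time where recorded; otherwise scheduled Day 1 assessments are taken as pre-dose).

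Use the same wording, with the extension's first dose as the anchor, for any LTE baseline, which protocol 12.3 defines and SAP 8.1 omits. SAP 8.8.2 can stay as it is. If the date cut-off was intended, keep it, declare and justify it in section 10, and reconcile it with SAP 4.1 and 8.4.2.

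The cost is one sentence in the SAP and a check that the derivation code matches it. No new data are needed. The parent schedule, or a count of parent values dated on the first-dose day, would show how many baselines the change affects.

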### 8.2 Protocol deviations

All major protocol deviations identified will be summarized by treatment group and overall.

A listing will include the inclusion/exclusion criteria violated at Screening and at Baseline Visits as well as other protocol deviations identified based on data recorded on the eCRF and/or protocol deviation Logs received from [REDACTED] Medical.

### 8.3 Subject disposition

The number of subjects in the following categories will be summarized overall and by treatment group:

# Statistical Analysis Plan (SAP)

- Subjects Screened
- Screen Failure(s)
- All Subjects as Treated (ASaT)

The number and percentage (based on ASaT) of subjects in each of the following disposition categories will be summarized overall and by treatment group:

- Completed treatment
- Prematurely discontinued the treatment and the reasons for discontinuation
- Completed study
- Prematurely discontinued the study and the reason for discontinuation

A listing will be provided for subjects who discontinued treatment or who discontinued study with reasons for discontinuation.

## 8.4 Demographics and baseline characteristics

The demographics and baseline characteristics, medical history, prior and concomitant medications will be summarized by treatment group and overall. Individual subject listings will be provided to support the summary tables.

### 8.4.1 Demographics

Age (years), height (cm), weight (kg) and other continuous demographic variables at Screening will be summarized descriptively. Gender, primary race, ethnicity and other categorical variables will be summarized.

Year of birth, age, gender, primary race, ethnicity, height, weight, and BMI will be listed as part of demographic listing

### 8.4.2 Baseline characteristics

Tender joint counts, swollen joint counts, PGA of disease activity, PtGA of disease activity, patient's pain assessment, HAQ-DI, hsCRP, ESR, and SF-36 at baseline will be summarized. Note baseline is the Baseline values from parent study.

### 8.4.3 Medical history

A summary of medical history will be presented by system organ class (SOC) and preferred term (PT) using the most recently available version of the Medical Dictionary for Regulatory Affairs® (MedDRA). A listing of medical history will be provided as well.

### 8.4.4 Prior and concomitant medications

Medications used in this study will be coded by using the World Health Organization Drug Dictionary and categorized as follows:

# Statistical Analysis Plan (SAP)

Prior medications and concomitant medications will be summarized descriptively using frequency tables by ATC class and preferred term by treatment group on the Safety Analysis Set. Prior medications are those with a stop date before the first dose of study drug, and concomitant medications are those with a stop date on or after the first dose of study drug or ongoing.

Details for imputing missing or partial start and/or stop dates of medication are described in [Section 7.2.2](#).

## 8.5 Extent of exposure

### 8.5.1 Treatment Duration

Duration of study drug exposure (in days) will be calculated as: last dose date – first dose date + 1 day, regardless of study drug interruption.

Study drug exposure will be summarised by treatment group using descriptive statistics.

Exposure to randomized study drug will also be categorised in intervals  $\leq 3$  months ( $<91$  days), 3-6 months (91-180 days), 6-12 months (181-365 days), 1-2 years (366-730 days), 2-3 years (731-1095 days),  $>3$  years ( $>1095$  days) and summarized by treatment group.

### 8.5.2 Treatment Compliance

Study drug compliance will be calculated as:  $100 \times \text{total number of doses administered} / \text{total number of doses planned to be administered}$  during the study drug exposure period. If only one syringe among the two is administered at a visit, the number of dose will be counted as 0.5. If both syringes are administered at a visit, the number of dose will be counted as 1. The total number of doses planned will count Weeks 0, 4, 8, 12, 16, 20, 24, 28, 32, 36, 40, 44, 48, 52, and all subsequent 4-weekly time points to Week 200. If a subject discontinues treatment, the total number of doses will be counted from Week 0 until the last dose before discontinuation.

Study drug compliance will be summarized by treatment group by the number of subjects (n), mean, SD, median, min, and max. They will also be summarized in categories “ $<80\%$  compliant” and “ $\geq 80\%$  compliant” using frequency tables.

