### 3.3 Study treatments and assessments

The maximum study duration from Baseline assessment to end of study is 208 weeks.

All subjects eligible for study participation will enter the extension study and continue to receive one of the 3 treatments as in the parent study. Study drug will be supplied as [REDACTED] and a subject at a visit is expected to receive two syringes packed in a kit. Below are the details:

- 200 mg q4 weeks arm: subjects will receive tildrakizumab 200 mg (two 1-mL injections of 100 mg/mL) at Baseline, Weeks 4, 8, 12, 16, 20, 24, 28, 32, 36, 40, 44, 48, 52, and all subsequent 4-weekly time points up to Week 200

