## Statistical Analysis Plan (SAP)

- 200 mg q12 weeks arm: subjects will receive tildrakizumab 200 mg (two 1-mL injections of 100 mg/mL) at Weeks 8, 20, 32, 44, 56, and all subsequent 12-weekly time points to Week 200, as well as placebo (two 1-mL injections) at interim 4-weekly time points commencing at Baseline of the Phase 2 parent study up to Week 196
- 100 mg q12 weeks arm: subjects will receive tildrakizumab 100 mg (one 1-mL injection of 100 mg/mL + 1 mL placebo) at Weeks 8, 20, 32, 44, 56, and all subsequent 12-weekly time points to Week 200, as well as placebo (two 1-mL injections) at interim 4-weekly time points commencing at Baseline of the Phase 2 parent study up to Week 196

If a subject misses a visit and/or a scheduled dose of IMP, the site must reschedule a visit to ensure the dose of IMP is taken as soon as possible within the visit window. If after 2 attempts to reschedule, the subject still is not able to take the dose, the Sponsor should be contacted to determine if the subject should be discontinued from the study.

Following the last subject's Week 52 visit or early termination prior to Week 52, all subjects will begin migrating to receive 100 mg tildrakizumab SC injection Q12 weeks in an open-label fashion.

A detailed description of procedures and assessments to be conducted during this study is summarized in the Schedule of Assessments in Table 1 below.

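### SAP 8.5.2 counts dummy kits and single syringes as study-drug doses, so in the two Q12W columns the compliance percentage mainly measures injection attendance, not tildrakizumab received (minor; descriptive table only)

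*SAP*

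**What the plan says.** SAP 8.5.2 divides doses administered by doses planned over the exposure period. For the denominator, "The total number of doses planned will count Weeks 0, 4, 8, 12, 16, 20, 24, 28, 32, 36, 40, 44, 48, 52", and it continues 4-weekly to Week 200. For a subject who stops treatment, the count ends at the last dose. For the numerator, "If both syringes are administered at a visit, the number of dose will be counted as 1", and "If only one syringe among the two is administered at a visit, the number of dose will be counted as 0.5". Nothing in the rule separates tildrakizumab from placebo. Results are shown by treatment group, and "They will also be summarized in categories" split at 80%.

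SAP 3.3 says what the kits hold. In the blinded period "a subject at a visit is expected to receive two syringes packed in a kit". In the 200 mg Q4W arm both syringes are active at every visit. In the 200 mg Q12W arm "subjects will receive tildrakizumab 200 mg (two 1-mL injections of 100 mg/mL) at Weeks 8, 20, 32, 44, 56" and every 12 weeks after that. The 100 mg Q12W arm receives "tildrakizumab 100 mg (one 1-mL injection of 100 mg/mL + 1 mL placebo) at Weeks 8, 20, 32, 44, 56" and so on. Both Q12W arms have these doses "as well as placebo (two 1-mL injections) at interim 4-weekly time points".

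No other active-drug measure is planned. Protocol 12.2.1 promises a descriptive compliance summary without a formula. SAP 8.5.1 takes exposure duration as last minus first dose date plus one day and ignores interruptions.

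**The concern.** The three treatment columns stand side by side under one label, but the percentage does not mean the same thing in each. In the Q4W column it is drug intake. In the two Q12W columns most of what it counts is attendance for placebo injections. A reader would naturally use this table to judge whether the safety, PK and antibody summaries for a regimen reflect subjects who received that regimen. For two of the three columns the 80% split can point the wrong way for an individual subject.

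The half-dose rule adds a separate problem in the 100 mg arm. Its active-visit kit holds one active and one placebo syringe, so a score of 0.5 corresponds to no possible drug intake at that visit. In the 200 mg arms one of two syringes at an active visit really is half the dose.

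**Working it through.** The documents give no compliance result to reproduce, so the check applies the SAP 8.5.2 rule to the SAP 3.3 schedule.

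**Inputs**
- Planned visits, Weeks 0, 4, …, 52: 52/4 + 1 = 14 (SAP 8.5.2).
- Active visits in the Q12W arms: Weeks 8, 20, 32, 44 = 4; dummy visits: 14 − 4 = 10 (SAP 3.3).
- Score: 0.5 per syringe given, 1 for both (SAP 8.5.2).
- Blinded period: at least 52 weeks of the extension (SAP 3.2.2).

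**Formula:** compliance = 100 × (0.5 × syringes given) / planned visits. Active drug = active dose received / active dose planned.

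| Q12W subject, Weeks 0–52 | SAP 8.5.2 | Class | Active drug |
|---|---|---|---|
| Misses 2 of 4 active visits, takes all dummies | 12/14 = 85.7% | ≥80% | 2/4 = 50% |
| Same, plus one dummy visit missed | 11/14 = 78.6% | <80% | 2/4 = 50% |
| Takes all active, misses 3 dummy visits | 11/14 = 78.6% | <80% | 4/4 = 100% |
| Misses all 4 active visits, takes all dummies | 10/14 = 71.4% | <80% | 0/4 = 0% |
| 100 mg arm: only the placebo syringe at each active visit | (10 + 4 × 0.5)/14 = 85.7% | ≥80% | 0/4 = 0% |
| 100 mg arm: one syringe at one active visit, all else given | 13.5/14 = 96.4% | ≥80% | 3/4 = 75% or 4/4 = 100% |

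The fifth row is an extreme case and only shows what the syringe rule allows. The last row shows that the 0.5 hides which side of 80% the subject is on.

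**Other horizons.** Under SAP 3.3, active visits never exceed one third of planned visits. Missing half the active drug while taking every dummy therefore costs at most one sixth, and the score is at least 83.3% at every horizon from Week 8 to Week 200. In the other direction, over Weeks 0 to 200 (51 planned visits) a subject with all active drug needs 11 missed dummies to fall below 80%: 40/51 = 78.4%.

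**Week 0.** SAP 3.3 starts active Q12W dosing at Week 8. The protocol Synopsis (Test Product, Dose and Mode of Administration) and Protocol 9.1.3.1.2 list a Week 0 dose. If Week 0 is active, 5 of the 14 visits are active. Missing half the active drug then scores (14 − 2.5)/14 = 82.1%, and all active drug with three dummies missed still scores 78.6%. Both directions hold at Week 52. The first fails at some other horizons: at Week 44, (12 − 2.5)/12 = 79.2%.

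**After the open-label switch.** The 4-weekly denominator to Week 200 is 200/4 + 1 = 51. A subject who switches after Week 52 and misses nothing has 14 blinded visits plus 13 open-label doses (Weeks 56, 68, …, 200). Counting each open-label injection as 1, that is 27/51 = 52.9%. With a switch after Week 104 (an assumed date) it is (27 + 8)/51 = 68.6%.

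**The case against.** The case for leaving the rule alone has real content.

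- **Blinding limits selective missing.** Subjects cannot tell active from dummy visits. If misses fall at random (an assumption), two misses among 14 visits are both active with probability C(4,2)/C(14,2) = 6/91 = 6.6%. Three misses are all dummies with probability C(10,3)/C(14,3) = 120/364 = 33%. Under the same assumption, expected visit compliance equals expected active-visit compliance. A reader might infer that the group means are biased; nothing in the documents supports that.
- **The first case needs near-perfect dummy attendance.** A reader might infer that any Q12W subject who misses half the drug is labelled compliant. One further full visit missed gives 78.6%, so such a subject can be so labelled, but need not be.
- **Little depends on the table.** The ASaT population needs one dose (SAP 6.1), no set excludes on compliance, and no tests are performed (SAP 8.6, 8.7).
- **Missed injections are visible elsewhere.** Departures from regimen go in the eCRF (Protocol 10.4). Deviations are summarised or listed (SAP 8.2), and concentrations are summarised by dose group (SAP 8.8.1).
- **Counting dummies fits the SAP's usage.** SAP 3.1 treats dummy placebo as IMP administration, and an all-injection percentage is a fair record of adherence under the blind.

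All of this bears on size. It does not alter the rule: the percentage is labelled study drug compliance, the 80% split is applied to it, and no other planned summary gives the share of active drug received.

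**Conclusion.** The point stands as a minor one. By the SAP's own rule and schedule, individual subjects in two of the three columns can land on the wrong side of the 80% cut in either direction, and a single syringe from a mixed 100 mg kit is scored at a value it cannot have. The Q4W column is unaffected.

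The effect stops at a descriptive table. A reader might infer that the safety conclusions or an analysis set are compromised; neither uses compliance. Nor will the Week 0 to 52 percentages dominate the final report. They matter mainly at the interim after the last subject's Week 52 visit (SAP 8.9) and for subjects who stop around then. In later tables the 4-weekly denominator carried past the switch outweighs them.

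The result assumes the blinded, dummy-controlled first year that SAP 3.2.2 and 3.3 describe. Protocol 9.1.1 ties the continued parent regimens to Week 52 of the parent study instead, and these texts must be reconciled. The Week 0 conflict changes some figures but neither direction at Week 52.

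**What to change.** Rewrite SAP 8.5.2 once, to deal with this and with the denominator after the switch:

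1. Define compliance as 100 × mg of tildrakizumab administered / mg planned for the regimen in force over the exposure period, and apply the 80% cut to that. The table's first and third subjects then score 50% and 100%, and both change category.
2. Take active or dummy status per visit from the unblinded regimen and the kit list. Protocol 10.2.4 describes a list of kit number and treatment, and expects the parent study to be unblinded by the first interim, so the blind is no obstacle.
3. For a partial visit with a mixed 100 mg kit, use the syringe given if it is recorded. The documents do not show that it is. If it is not, flag the visit and report both bounds (0% and 100% of that dose) in place of 0.5.
4. Keep the present all-injection percentage as a separate line named *injection visit adherence*.
5. Before planned mg is fixed, reconcile SAP 3.3 with the protocol's Week 0 dose. Which of them is right is for the sponsor to settle.

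The cost is SAP wording, a programming change and one merge with the kit list. No new data collection is needed unless the sponsor wants syringe-level records for partial visits.
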